Initial treatment: surgery, type of surgery, margins, tumor spillage, residual cellularity, neo/adjuvant systemic treatment indication (start and stop date, type), radiation therapy, other treatment (cryotherapy, radiofrequency, embolisation), clinical trial inclusion

Metastatic relapse/event characteristics: PS, location of first metastasis, number of sites

Treatment of metastatic event: systemic treatment (PS molecule used, start and stop date, best RECIST response, date of progression, clinical trial), locoregional treatment (surgery, radiotherapy, cryotherapy, radiofrequency, embolisation), clinical trial.

Dates: Birth, initial diagnostic, surgery of primary, local relapse, metastatic relapse, start of each chemo line, date of progression for each chemo line, last contact, death

Samples: Molecular cytogenetics : method (RT PCR, FISH), transcript (FOR EWING SARCOMA ONLY)

Survival data

Median follow up

Progression free survival (PFS): PFS defined as the time from the systemic treatment onset to progression or death due to any cause, whichever comes first. When neither death nor progression is observed, PFS is censored at the date of last patient contact.

Time to next treatment (TNT): TNT defined as the time from the systemic treatment onset to the next treatment or death due to any cause, whichever comes first. When neither death nor new systemic therapy is observed, TNT is censored at the date of last patient contact.

Overall survival (OS): OS is defined as the interval between the diagnosis of first tumor event and the time of death. OS in the unresectable locally advanced setting is defined as the interval between the diagnosis of unresectable locally advanced setting (at diagnosis or relapse) and the time of death. OS in the metastatic setting is defined as the interval between the diagnosis of metastatic disease (at diagnosis or relapse) and the time of death. When death is not observed, OS is censored at the date of last patient contact.

STATISTICS

Statistical analysis of the baseline demographics and clinical outcomes will be based on all data available up to the cut-off date of August 31, 2021.

Descriptive statistics will be used to show the distribution of variables in the population.

The variables included in the univariate and multivariate analyses are the descriptive data including:

- type of chemotherapy used (poly vs mono, class of chemo: TKI, Ifosfamide, other)
- locoregional treatment of metastasis,

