- inclusion in a clinical trial in first line,
- at least one inclusion in a clinical trial during metastatic stage,
- use of off-label drug at least once during metastatic stage

Multivariate logistic regression models will be used to identify biological and clinical factors associated with the type of treatment received after 1st line: in second, third, 4th line, and with the probability of survival 5 years after the diagnosis of metastases.

Follow-up times will be described as median values based on the inverse Kaplan–Meier estimator.

Prognostic factors of TNT for each line (1st, second, Third) and OS will be identified using Cox proportional hazard models.

The correlation between TNT and OS will be evaluated at each of the four first-lines of metastatic chemotherapy by a Spearman rank correlation coefficient and expressed as a value between 0 (no association) and 1 (perfect association). We will use a reviewed copula-based approach that introduces an iterative multiple imputation method for the estimation of the correlation coefficient. The data will be analyzed using the SAS v9.3 and R v3.3 software packages.

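### Two covariates defined over the whole metastatic stage have no timing rule: read as ever/never, they put immortal time into metastatic OS and later-line information into any TNT-by-line model they enter

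*Combined protocol and SAP*

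**What the plan says.** The covariate list in STATISTICS opens with "The variables included in the univariate and multivariate analyses are the descriptive data including" and is not tied to any one endpoint. Two of its items are "at least one inclusion in a clinical trial during metastatic stage" and "use of off-label drug at least once during metastatic stage". Neither has a date of assessment. The item just before them, trial inclusion at first line, does belong to a line.

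The models are described as follows: "Prognostic factors of TNT for each line (1st, second, Third) and OS will be identified using Cox proportional hazard models". Logistic regression is also planned for factors associated "with the probability of survival 5 years after the diagnosis of metastases".

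The clocks are set under Survival data. "OS in the metastatic setting is defined as the interval between the diagnosis of metastatic disease" and the time of death, and "TNT defined as the time from the systemic treatment onset to the next treatment or death due to any cause".

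Under VARIABLES, the data for each metastatic event include "systemic treatment (PS molecule used, start and stop date, best RECIST response, date of progression, clinical trial", and the start of each chemotherapy line is dated. The document mentions no time-dependent covariate, no landmark and no restriction to exposures known when a line begins.

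**The concern.** A patient first treated in a trial at third line must be alive and on treatment at third line. If that patient is classed as exposed from metastatic diagnosis, all the survival before third line is credited to the exposure. A patient who dies during first line cannot be classed as exposed through a later line. The 5-year survival model has the same fault if the variables enter it.

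TNT at line 1 has ended before line 2 begins. An ever/never value that depends on line 2 or later therefore tells the line-1 model something that happened after its outcome.

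Factors associated with TNT and prognostic factors for OS are named secondary endpoints. A published statement that trial inclusion or off-label use goes with longer or shorter survival could come from the coding alone.

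**Working it through.** The plan gives no figure on this point, so there is nothing to reproduce. The check has an algebraic part and a simulation part.

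**1. Immortal time, by algebra.** Let d1 and T1 be deaths and person-time after first exposure, d0 and T0 deaths and person-time while unexposed, and W > 0 the part of T0 lived before exposure by patients who are later exposed. Ever/never coding moves W across and moves no deaths:

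- correctly allocated: (d1/T1) / (d0/T0)
- ever/never: (d1/(T1+W)) / (d0/(T0−W))
- ratio of the second to the first: [T1/(T1+W)] × [(T0−W)/T0], which is always below 1.

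This component has a fixed direction, towards apparent benefit. It shows that ever/never lies below plain time-dependent coding. It does not show that ever/never lies below the true value, because plain time-dependent coding may itself be off (step 3).

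**2. Inputs to the simulation.** From the documents: diagnoses 2008–2018 and cut-off 31 August 2021, giving follow-up of 32 months (end of 2018) to 164 months (start of 2008), counted from metastasis as an approximation; and 400–500 informative patients, taken as 450. Assumed, not in the documents: median OS 12, 18 or 24 months; median 5 months per line; up to 8 lines; exposure at random with probability 0.1, 0.2 or 0.3 per line; frailty (a patient-level multiplier on all rates); and a share of patients who never leave first line and do not die before cut-off. True effect: none. There were 198 settings of 112,500 patients each.

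**3. Ever/never OS hazard ratio under the null (true value 1).**

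| Frailty variance | 0% never leave line 1 | 5% | 10% | 15% | 20% |
|---|---|---|---|---|---|
| 0 | 0.39–0.61 | 0.62–0.74 | 0.78–0.83 | 0.89–0.95 | 0.98–1.13 |
| 0.5 | 0.60–0.75 | 0.75–0.84 | 0.89–0.92 | 0.97–1.05 | 1.04–1.18 |
| 1.0 | 0.79–0.86 | 0.91–0.94 | 0.99–1.07 | 1.06–1.19 | 1.12–1.32 |
| 1.5 | 0.93–0.97 | 0.99–1.10 | 1.07–1.22 | 1.11–1.33 | 1.18–1.47 |

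The first row is for constant rates. With homogeneous patients and deaths early or late within a line, the range widens to 0.37–0.68. A simulation limited to 4 lines, with median OS 12–36 months, exposure 10% or 25% per line and no heterogeneity, gave 0.58–0.79 for ever/never and 0.99–1.02 for plain time-dependent coding.

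The upward movement across the table is a second bias. Patients who do well start fewer lines and so get fewer chances of exposure. Ever/never coding does not cause it: time-dependent coding without line number gave 0.79–2.45 across the settings.

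**4. 5-year survival odds ratio, if the variables enter.** Homogeneous 3.09–7.71; frailty alone 0.99–2.39; never-leavers alone 0.58–2.24; both 0.57–1.54.

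**5. TNT hazard ratio, if the variables enter.** For line 1: 0.99–1.03 under constant rates, 0.80–0.90 with deaths early in a line, 1.19–1.29 with deaths late, and 1.08–2.11 with frailty, never-leavers or both. For lines 2–3: 0.86–1.33. There is no fixed direction.

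**6. Corrected analyses under the null.** OS, time-dependent with current line number: 0.98–1.02. OS, 6-month landmark stratified by line reached: 0.97–1.03 (0.96–1.65 without line). TNT with values known at line start: 0.97–1.03. False-positive rates of the corrected OS models at 450 patients were 2–10% per setting, mean 5%.

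**7. What the correction leaves.** If the better-prognosis half has 2–3 times the odds of exposure, the corrected OS models still give 0.76–0.91; if the worse half does, 1.10–1.38.

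**The case against.** The plan does not assign these variables to a model, nor say that they are fixed in time, and a Cox model can take time-dependent covariates. That stands: ever/never is the natural reading of the wording, not a stated choice. For line-1 TNT, the timed first-line trial covariate already on the list does the job properly, and under constant rates the ever/never version does little harm.

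A reader might infer that ever/never coding biases OS in a wholly unpredictable direction. The documents and the algebra do not support this. The immortal-time part always favours exposure. Only the net of that and the fewer-lines bias lacks a fixed sign. Every hazard ratio above 1 in the table also needed patients who stay in first line and survive to cut-off. The inclusion criteria pool three histologies, so varied prognosis is plausible, but nothing in the documents supports that particular group or its size.

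A reader might infer the opposite, that the result must be spurious benefit. That holds for homogeneous patients and for frailty alone in these runs, but it cannot be guaranteed for this cohort.

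The remedy also has a cost in interpretation. Current line number comes after exposure and may lie on the causal path. In illustrative runs where exposure halved the progression rate within a line and the death rate rose 1.5- or 2-fold per line, the line-stratified hazard ratio was 1.02 and 1.07 (0.98 and 1.03 with no effect), so a real benefit was hidden. This argues for showing both analyses, not for leaving the timing open.

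**Conclusion.** The concern holds in a limited form. Two covariates enter the regression analyses without a timing rule. Read as ever/never, they carry immortal-time bias towards exposure in metastatic OS, and in the 5-year model if they enter it. They also put later information into any TNT-by-line model they enter. The net OS error has no guaranteed sign.

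Sizes rest on the assumptions listed above. At 450 patients, a significant null OS result appeared in 88–100% of replicates with homogeneous patients (all benefit); in 67–100%, 23–58% and 3–10% at the three frailty levels; and in up to 86% (all harm) at frailty 1.5 with 20% never-leavers. Treat these as upper figures: the 400–500 patients include unresectable locally advanced disease, and the document does not give the metastatic count.

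This should be fixed before analysis. Confidence is medium. The descriptive primary endpoint is unaffected.

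**What to change.** Add to STATISTICS, for both variables:

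1. **OS.** Code as time-dependent from the start of the first qualifying line, stratified by or adjusted for current line number. Alternatively use a landmark (for example 6 months), with exposure known by then and stratification by line reached. Report results with and without line adjustment. State that current line may lie on the causal path, so the estimate is an association that may miss an effect acting through delayed progression.
2. **TNT at line k.** Use only values known at the start of line k. For trial inclusion at line 1, the existing first-line covariate already does this.
3. **5-year survival.** Use only factors known at metastatic diagnosis, or at a landmark among patients alive then. Otherwise drop the two variables.
4. **Interpretation.** State that confounding by patient selection remains, and adjust for PS at line start where recorded.

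Also confirm in the data dictionary whether local treatment of metastases and chemotherapy type can arise after metastatic diagnosis. If so, handle them the same way for OS.

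The cost is SAP wording and modest programming. Line start dates and trial participation per systemic treatment are already collected; off-label status must be derived from the recorded molecule. A 6-month landmark loses patients who die before it (9–35% across the simulated settings).

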ID: IB2019-METABONE

Patterns of Care and Outcomes in Patients With Metastatic Bone Tumors (METABONE)

NCT03963531

Jan 5, 2007

INCLUSION

- Patients age > 12 year old at initial diagnosis
- Histology of Ewing's sarcoma type, osteosarcoma, chondrosarcoma
- Diagnostic of primary event between 2008 and 2018
- Diagnostic of unresectable locoregional disease where palliative treatment is indicated, or metastatic disease
- Treatment and monitoring made in one of the GSF-GETO centers, with follow up data on treatment received available.

OBJECTIFS

I. OBJECTIVES AND ENDPOINTS

The primary objective of the METABONE study is to give a retrospective descriptive analysis of clinico-biological profiles, patterns of care and modalities of treatment of patients with unresectable locally advanced and/or metastatic malignant bone tumors in a real-life national setting.

The primary endpoint is description of initial and local/metastatic relapse events management of adult patients with the diagnosis of Ewing's sarcoma, osteosarcoma, chondrosarcoma, made in one of the centers of the RESOS network between 2008 and 2018, in terms of therapeutic strategies including chemotherapy, surgery, radiotherapy, interventional radiology.

Secondary endpoints

- Description of systemic treatments received in the palliative setting in terms of **PFS** (progression free survival) and **TNT** (Time to next treatment)
- **Overall survival** from unresectable locally advanced and/or metastatic stage
- Identification of **factors associated with PFS and TNT** for molecules used in the unresectable locally advanced and metastatic setting
- Identification of **prognostic factors for overall survival** (OS) in the unresectable locally advanced and/ metastatic setting

II. METHODS

PATIENTS

We estimate the population size in the database of about 2800 patient cases.

We seek to include 800 patients to be screened in the present study.

We aim to get about 400 to 500 informative patients with unresectable locally advanced or metastatic disease.

VARIABLES

Variables collected will be those of the **CONTICABONE DICTIONNARY**

Descriptive data

Centers, number of patients per center

Initial patients characteristics at diagnostic: Age at diagnosis, gender, PS at diagnosis, previous history of specific disease (Li Fraumeni, Multiple Exostosis)

Tumor characteristics at diagnostic : location, side, size, multifocality, LR spread and type, stage N M, histology, grade, previous radiation area,

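### The shared covariate list has no timing rule, so the line-2 to line-4 treatment-type models may take as predictors variables set by the modelled line or by later lines

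*Combined protocol and SAP*

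**What the plan says.** The Statistics section introduces a single list: "The variables included in the univariate and multivariate analyses are the descriptive data including". The treatment items that follow include:

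- "type of chemotherapy used (poly vs mono, class of chemo: TKI, Ifosfamide, other"), with no treatment line given;
- locoregional treatment of metastases, undated;
- "inclusion in a clinical trial in first line", which precedes lines 2 to 4;
- "at least one inclusion in a clinical trial during metastatic stage", an ever/never flag;
- "use of off-label drug at least once during metastatic stage", another such flag.

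The next paragraph specifies the models: "Multivariate logistic regression models will be used to identify biological and clinical factors associated with the type of treatment received after 1st line". It names lines 2, 3 and 4, and the same sentence adds a second logistic outcome, being alive 5 years on from the finding of metastases. The categories of treatment type are not defined. No sentence assigns covariates to particular models, removes a listed variable from a model in which it is the outcome, or fixes covariates at the start of the line being modelled.

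On size, the Patients section says "We aim to get about 400 to 500 informative patients with unresectable locally advanced or metastatic disease". The numbers reaching lines 2, 3 and 4 are not given.

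**The concern.** Two things go wrong if the list is applied literally to the treatment-type models.

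First, chemotherapy type can stand on both sides of the equation, because the covariate carries no line and the outcome is treatment type at line k.

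Second, the two flags look forward. An off-label drug or a trial entry at line k sets the flag, and so does one at a later line. The flag is then a common consequence of the outcome and of anything that governs how many further lines a patient receives. Conditioning on it induces an association between those factors and the outcome.

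These are the only planned models of what drives treatment choice after first line, in a study whose primary objective is to describe patterns of care. A factor such as performance status could be reported as influencing the choice of class when it only influences how many lines a patient lives to receive.

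**Working it through.** The plan states no odds ratio, event count or power for these models, so there is no figure of its own to reproduce. I checked the consequence under assumed inputs.

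**Same-line type as covariate.** In simulated data with 250 patients at line 2, entering line-2 class as a predictor of line-2 class gives a singular matrix and no fit. Entering prior-line class gives an ordinary finite coefficient (-0.34, SE 0.34).

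**Off-label flag: assumptions, none from the documents.** The outcome is TKI versus other at line 2. TKI probability is 30% in both performance-status groups, so the true odds ratio is 1.0. 40% have poor status. The chance of reaching line 3, and then line 4, is 0.6 per step (good) against 0.3 (poor), or 0.7 against 0.2. Off-label probability is a for a TKI and b for other drugs. 30% receive a TKI at each later line.

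**Formula.** Let q be the probability of no off-label use at any line other than line 2. Then P(flag = yes | TKI) = 1 - (1 - a)q and P(flag = yes | other) = 1 - (1 - b)q. Among flag-negative patients q cancels and the odds ratio is exactly 1. Among flag-positive patients, poor versus good:

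OR = {[1 - (1 - a)q_poor] / [1 - (1 - b)q_poor]} ÷ {[1 - (1 - a)q_good] / [1 - (1 - b)q_good]}

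**Worked case: a = 100%, b = 10%, no off-label use at line 1.** Off-label probability at a later line is 0.3 × 1 + 0.7 × 0.1 = 0.37, so 0.63 have none.

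- Reach 0.6 v 0.3: q_good = 0.4 + 0.378 × 0.778 = 0.694; q_poor = 0.7 + 0.189 × 0.889 = 0.868. OR = (1 - 0.9 × 0.868)⁻¹ ÷ (1 - 0.9 × 0.694)⁻¹ = 0.375/0.219 = 1.72.
- Reach 0.7 v 0.2: q_good = 0.3 + 0.441 × 0.741 = 0.627; q_poor = 0.8 + 0.126 × 0.926 = 0.917. OR = 0.436/0.175 = 2.49.

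With a = 100%, no TKI patient is flag-negative, so these are also the fitted values. Otherwise the main-effects model averages the two strata. At 90% v 10% and reach 0.6 v 0.3, the flag-positive odds ratio is (0.912/0.210) ÷ (0.928/0.356) = 1.67, and the fitted value is 1.52.

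Fitted odds ratio for performance status, from logistic fits to the expected cell proportions (true value 1.0; each range spans the two reach scenarios):

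| Off-label, TKI v other | No off-label use at line 1 | Line 1 also counted, at rate b | Empty cell |
|---|---|---|---|
| 100% v 10% | 1.72 to 2.49 | 1.48 to 1.91 | yes |
| 90% v 10% | 1.52 to 2.03 | 1.36 to 1.67 | no |
| 60% v 20% | 1.16 to 1.28 | 1.10 to 1.17 | no |
| 30% v 30% | 1.00 | 1.00 | no |

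Counting line 1 means multiplying both q values by (1 - b). Without the flag the odds ratio is 1.0 in every row.

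**Finite samples.** In 400 simulated data sets with 250 patients at line 2 (flag over lines 1 to 3, half reaching line 3), an empty cell occurred in every data set at 100% v 10% and in none at 90% v 10%. With 150 patients it occurred in about 3% at 90% v 10%. The median odds ratio of the flag itself at 250 patients was about 25 at 90% v 10%, 3.1 at 60% v 20% and 1.0 at 30% v 30%.

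**The case against.** The strongest reply is that the list was not written for these models. The same sentence covers a logistic model of 5-year survival, and Cox models of TNT and OS follow; chemotherapy type is a natural covariate there and not the outcome. The treatment-type sentence asks for biological and clinical predictors, which may be meant to leave treatment variables out. Chemotherapy type without a line may mean first or prior line. If same-line type were entered, the fit would fail visibly and would not yield a plausible wrong answer. All of this stands, so outcome-as-covariate is one permitted reading, not an established fact.

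It does not dispose of the flags. Their wording covers the whole metastatic stage, so a prior-line reading is not available for them, and the list is declared for the multivariate analyses without exception. The treatment items spelled out in it also make it hard to assume that treatment variables are excluded.

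A reader might also infer that chemotherapy class determines the off-label flag, so that a cell is empty by definition. The documents never link a class to off-label or trial status; the empty cell appears only under the assumed 100%. Nor does it follow that null factors will generally appear significant. With 250 patients at line 2, 30% on a TKI, 40% with poor status and all TKIs off-label, a null factor biased to about 1.3 was rejected in about 12% of replicates, and one biased to about 1.66 in about 30%. Type I error is inflated, but most replicates were not significant.

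Finally, the treatment-type models serve no listed endpoint: the primary endpoint is descriptive, and the secondary ones concern PFS, TNT and OS. That limits the damage without making the models right.

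**Conclusion.** The point holds as a missing timing and model-assignment rule that, followed as written, can give wrong odds ratios. Bias needs two conditions together: off-label or trial use differs by treatment type, and the factor of interest affects how many later lines are reached. It does not need separation. Across the unequal off-label rates examined, a null performance-status factor is estimated at about 1.2 to 2.5, or 1.1 to 1.9 when first-line off-label use also sets the flag. It vanishes when off-label use is equal across classes. The calculation is for the off-label flag; the trial flag has the same structure, but I have not put a figure on it.

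All sizes rest on assumed class frequencies, off-label rates and attrition, none of which the documents give. They do not support the stronger inference that these models are necessarily circular or necessarily separate. The change is worth making before analysis, but it does not touch the descriptive primary endpoint.

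**What to change.** Add one sentence to the Statistics section: the treatment-type model for line k uses patient and tumour variables plus treatment variables known before line k starts (prior classes, prior trial inclusion, prior off-label use, prior locoregional treatment). It excludes same-line chemotherapy type and both flags covering the whole metastatic stage. First-line trial inclusion can stay, since it precedes lines 2 to 4. Define the outcome categories for each line at the same time.

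The cost is that sentence and some recoding. The Variables section already collects the molecule, start and stop dates and trial status for systemic treatment, so the prior-line variables can be built without new data collection.

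### The 5-year logistic survival model has no rule for patients alive with under 5 years of follow-up, and after August 31, 2016 only deaths can be classified (minor)

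*Combined protocol and SAP*

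**What the plan says.** All references are to the combined protocol and SAP.

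- **STATISTICS.** Multivariate logistic models are planned for two purposes: type of treatment after first line, and factors associated "with the probability of survival 5 years after the diagnosis of metastases". Analyses are "based on all data available up to the cut-off date of August 31, 2021".
- **INCLUSION.** The entry window is "Diagnostic of primary event between 2008 and 2018". Follow-up is required only in the sense of "with follow up data on treatment received available"; no minimum length is set.
- **Survival data.** OS in the metastatic setting is "the interval between the diagnosis of metastatic disease (at diagnosis or relapse) and the time of death", so the time origin can fall after 2018. The censoring rule is "When death is not observed, OS is censored at the date of last patient contact".
- **STATISTICS, other methods.** Cox models serve TNT and OS. The only imputation is an "iterative multiple imputation method for the estimation of the correlation coefficient", which concerns the association between TNT and OS.
- **STATISTICS, listed factors.** Covariates include chemotherapy class, off-label use and "inclusion in a clinical trial in first line".

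**The concern.** A logistic model needs each patient's status at 60 months to be known. A patient alive at last contact with under 5 years of follow-up has no such status. The OS censoring rule gives that patient a censored time, not a yes or no, and the imputation is tied to a different analysis. The analyst must therefore choose a rule that the plan does not state.

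The missing statuses are not spread evenly. Among patients with late metastases, only deaths can be classified. If unknowns are dropped, those retained from the late period are all dead at 5 years. If unknowns are coded dead, the whole late period has no survivors. If they are coded alive, the late period has too many. Any factor more common in late patients takes on part of that artefact, and its direction depends on the unstated rule. The model's purpose is to identify factors, so a spurious or weakened association is what is at stake.

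**Working it through.** The plan gives no figure to reproduce for this model: no assumed 5-year survival and no sample size reasoning. The check has a part that follows from the dates and a part that rests on assumptions.

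**1. Dates (from the document)**

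- Cut-off August 31, 2021 minus 5 years = August 31, 2016.
- September 1, 2016 to December 31, 2018 = 122 + 365 + 365 = 852 days. The window 2008-2018 has 4,018 days. 852 / 4,018 = 21.2% cannot reach 5 years if all are metastatic at diagnosis and accrual is even. If 2018 is excluded: 487 / 3,653 = 13.3%.
- Metastases on December 31, 2018 allow 974 / 365.25 = 2.67 years of follow-up at most.

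**2. Share with unknown 5-year status (assumptions)**

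Assume even accrual, exponential OS with median 18-24 months and no loss before the cut-off. If all are metastatic at diagnosis, with λ = ln 2 / median:

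unknown share = [exp(−2.67λ) − exp(−5λ)] / (11λ)

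- Median 18 months, λ = 0.462: (0.2916 − 0.0992) / 5.083 = 3.8%.
- Median 24 months, λ = 0.347: (0.3969 − 0.1768) / 3.812 = 5.8%.

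If 50-70% become metastatic later, with an assumed median delay of 18 months, simulation gives 7.5-12.0%. Of 450 patients (the midpoint of the 400-500 target), that is at most 17-26 or 34-54. The target includes locally advanced disease without metastases; if 300 are metastatic (assumed), the counts are 11-17 or 23-36. Loss to follow-up of 3% a year would raise the shares to 9.0-11.9% and 12.3-17.4%.

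**3. Effect on odds ratios (simulation, same assumptions)**

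The factor rises from 20% to 60% over 2008-2021. Results are unadjusted.

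| Rule for unknowns | Factor with no effect (truth 1.00) | Bias in standard errors, no effect, 450 metastatic | Factor with hazard ratio 0.6 (true odds ratio 2.5-3.0) |
|---|---|---|---|
| Dropped | 0.82-0.88 | 0.3-0.6 | 11-15% too low |
| Coded alive | 1.07-1.32 | 0.3 to about 1 | 0-6% too high |
| Coded dead | 0.77-0.85 | 0.4-0.8 | 20-32% too low |

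With unknowns dropped, the standard error of the log odds ratio is 0.29-0.40 with 450 metastatic patients. For example, ln 0.83 = −0.19, and 0.19 / 0.31 is about 0.6 standard errors. The standard-error column applies to the factor with no effect only.

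- Weaker trend, 30% to 50%, no effect: 0.91-0.94 (dropped), 1.04-1.15 (alive), 0.88-0.92 (dead).
- Factor unrelated to calendar time, unknowns dropped: 1.00 under no effect; a 1-2% shift with hazard ratio 0.6.
- Date of metastasis added as a linear term: dropped and dead-coded results return to 0.97-1.03 of truth. Alive-coded results stay 4-16% too low with hazard ratio 0.6.

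**4. Candidate fixes, same 20% to 60% factor**

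- Restriction to metastases by August 31, 2016: within about 1% of truth, with or without a real effect.
- Pseudo-observations at 60 months on all metastatic patients: within about 1%.
- One unconditional censoring curve as weights on all patients: 0.84-0.87 under no effect, no better than dropping.

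**The case against.** The strongest reply is that the unadjusted figures overstate what the planned model would show. The model is multivariate, the plan says its covariates are the descriptive data, and the dates of diagnosis and metastatic relapse are listed in that block. One linear term for date of metastasis nearly removes the bias if unknowns are dropped or coded dead. This stands as a limit on size. It does not close the gap: the plan does not expressly name that date as a covariate here, and adjustment does not rescue coding as alive when the factor has a real effect.

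Second, the bias for a factor with no effect is mostly below one standard error, and with 300 metastatic patients only about 20-42 five-year survivors would be observed, so the model is imprecise under any rule. This also stands. A systematic error whose sign depends on an unstated choice is still worth removing when removal is cheap.

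Third, a reader might infer more than the documents support:

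- That the results for trial inclusion or drug class will be biased. Nothing shows that these factors change in frequency over the period; they only could.
- That the OS findings are compromised. The listed secondary endpoint on prognostic factors for OS is served by Cox models, with a stated censoring rule.
- That a reported 5-year survival figure will be too low. Dropping unknowns would turn a true 9.9% into 7.4-8.2%, but the plan does not say such a figure will come from this model.

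**Conclusion.** The gap is real and minor. The date limit and the dead-but-never-alive asymmetry follow from the document alone, and no stated method covers them for this model. Bias is possible, not demonstrated: it needs an unsuitable rule for unknowns and a factor that tracks calendar time. The sizes shown rest on assumed accrual, survival, relapse delay and trend, and the unadjusted figures are near a worst case for a multivariate model that includes date of metastasis. Factors unrelated to calendar time are essentially unaffected when unknowns are dropped. The descriptive primary endpoint, the Cox analysis of OS and the logistic models for type of treatment are outside this concern.

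**What to change.** Add one or two sentences to STATISTICS:

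- Fit the 5-year logistic model only in patients whose metastases were diagnosed on or before August 31, 2016.
- For those lost before 60 months, use inverse-probability-of-censoring weights conditional on date of metastasis and covariates. With 3% a year loss, restriction alone gave 9.0-9.1% against a true 5-year survival of 9.9%; adding weights recovered 9.9%.
- Optionally, as a sensitivity analysis, use pseudo-observations at 60 months with a logit link on all metastatic patients.
- Report any 5-year survival probability by Kaplan-Meier.

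The dates needed are already collected. Restriction removes no patient who could be observed alive at 5 years. Under the assumptions above it keeps 79% of metastatic patients if all are metastatic at diagnosis, or 68-71% with later relapse, and confidence intervals are about 1-4% wider than when unknowns are dropped. The price is scope: the restricted model does not describe metastases diagnosed after August 2016.
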